***Table 8: Dose Delays and Modifications for cGVHD (see NIH cGVHD Severity Score in Appendix G)***

Mild cGVHD	The presence of new or worsening Mild cGVHD should warrant standard of care therapies for commensurate GVHD level and does not require any dose modifications to the flotetuzumab.
Moderate cGVHD	The presence of new or worsening Moderate cGVHD when baseline assessment prior to flotetuzumab was rated as Mild or better should warrant standard of care therapies

	for commensurate GVHD and the does not require any dose modifications to the flotetuzumab. Persistent Moderate cGVHD not improving with SOC interventions and supportive cares within 24-48 hours requires a 25-50% dose reduction in flotetuzumab with continued SOC interventions, supportive cares and continued monitoring of cGVHD severity. Uptitration of flotetuzumab to target dose may be attempted as per CRS protocol upon improvement of cGVHD to Mild or better. However, persistent Moderate cGVHD not improving with SOC interventions and with 25-50% dose reduction after 48-72 hours requires an immediate hold of flotetuzumab. Reinitiation of flotetuzumab with resolution of cGVHD severity to Mild or better can be attempted, resuming at 25-50% of the target dose and uptitration as per CRS protocol.
Severe cGVHD	The presence of Severe cGVHD should warrant standard of care therapies for commensurate GVHD and requires immediate hold of flotetuzumab. SOC interventions and supportive cares should be continued with daily assessment of cGVHD Grade. Reinitiation of flotetuzumab should not be attempted.

## 6.5 Tumor Lysis Syndrome

Tumor lysis syndrome (TLS) is the most common disease-related emergency encountered by physicians caring for children or adults with hematologic cancers. Characteristic findings are hyperuricemia, hyperkalemia, hyperphosphatemia, and hypocalcemia. These electrolyte and metabolic disturbances can progress to clinical toxic effects, including renal insufficiency, cardiac arrhythmias, seizures, and death due to multi-organ failure.

Prophylaxis for TLS should be administered for patients with AML. Aggressive hydration, allopurinol, and oral phosphate binders should be implemented starting preferably 24 hours before flotetuzumab administration. Serum chemistries should be closely monitored during flotetuzumab administration in accordance with institutional standards for the treatment of acute leukemia. If TLS is observed, rasburicase should be considered for management as per institutional standards. Patients who develop TLS should be monitored closely for abnormal serum chemistries or signs of end organ damage and treated appropriately.

## 6.6 Neutropenic Sepsis/Fungemia

While there is no evidence that flotetuzumab targets and depletes neutrophils in vitro in human samples or decreases circulating neutrophils in monkeys receiving the drug, caution should be exercised in assessing the possibility of infections. Early initiation of empiric broad-spectrum antimicrobials is recommended in the event of fever.

Several monotherapy or multicomponent regimens have been employed. Investigators should employ these agents in compliance with best medical practices and institutional guidelines and standards. If fever persists for 4 to 7 days, an echinocandin or liposomal amphotericin B should be considered. The use of recombinant hematopoietic growth factors in AML is controversial. Their use is specifically prohibited in Cycle 1. However, beyond Cycle 1, while discouraged, their use is not specifically prohibited by this protocol and they may be employed at the discretion of the Investigator.

## **6.7 Immune-related Adverse Experiences**

Immune checkpoint blockade has been associated with several syndromes resulting from the breaking of immunological tolerance. Although not observed in non-clinical studies to date, similar immunomodulation might be expected with flotetuzumab. These syndromes include: pneumonitis, colitis, autoimmune hepatitis, arthritis, glomerulonephritis, myocarditis and cardiomyopathy, hypophysitis, or thyroiditis. Their occurrence dictates interruption, and potentially discontinuation, of study drug administration pending further evaluation.

## **6.8 Neurotoxicity Monitoring**

Neurotoxicity, including changes in mental status, has been reported with other T-cell directed therapies including chimeric-antigen receptor (CAR)-T cells and CD3xCD19 based bispecific antibodies such as blinatumomab. The exact mechanism of the toxicity is unknown. As a result, additional monitoring of patients receiving flotetuzumab is indicated. An alteration in mental status refers to general changes in brain function, such as confusion, amnesia, loss of alertness, disorientation, defects in judgment or thought, and disruption in perception and psychomotor skills. Patients should be monitored for changes in mental status or other potential neurotoxic events and should be evaluated for orientation to time, place and person at baseline prior to treatment with flotetuzumab and at regular intervals during therapy.

Any suspected neurotoxic event should prompt full evaluation including imaging studies, lumbar puncture and neurological consultation as indicated to rule out other causes. The incidence of CNS involvement by AML is low and routine lumbar puncture is not generally considered indicated. Patients with known, active CNS leukemia are excluded from the study and those with suspected disease must be evaluated by lumbar puncture prior to enrollment. See Appendix E for grading, evaluation and management of neurotoxicity.

## **7.0 CORRELATIVE STUDIES**

Patient material will be obtained at Barnes-Jewish Hospital or in the Siteman Cancer Center. Samples will be identified with the patient's name, date of birth and clinic or hospital number. The Stem Cell Transplantation Core analyst or a designated person will be responsible for removal of this information from the sample container and its replacement by a label containing a Unique Patient Number (UPN) and sample number. Any paper copies of the master code listing UPN and

sample numbers with the patient names will be kept in a locked storage. Any electronic copies of the master code will be kept in a secured network. Access to either paper or electronic copies will be restricted to the Principal and Sub-Investigators of this study and associated study personnel.

Stem Cell Transplantation Core personnel will be responsible for transport of the specimens to the pre-defined laboratories for processing. Specimens will be identified by UPN and sample number and will be processed and stored at the pre-defined lab. Each lab will be responsible for sample processing, storage, and delivery of specimens according to established standard operating procedure documents generated for the purpose of this trial. The pre-defined lab will be responsible for establishing and maintaining standardized operating procedures as it relates to sample handling.

All samples should be sent to:

Siteman Cancer Center Tissue Procurement Core Facility  
[name]  
[name]  
[contact]  
[contact]  
Email: [[contact]](mailto:[contact])

**OR**

[name] Laboratory  
Washington University School of Medicine  
[name]  
[name]  
Contact Person: [name]  
[contact]  
Email: [[contact]](mailto:[contact])

During each BM Bx, samples for correlative studies will be obtained and banked at the following time points: (2-3 ml bone marrow aspirate in 1 EDTA tube per time point):

- Screening/Baseline
- Cycle 1 Day 14 (optional, at discretion of Principal Investigator.)
- Cycle 1 Day 28
- Cycle 2 Day 28
- At relapse or progression of disease

In addition, peripheral blood will be obtained from patients at these time points:

- Cycle 1 Day 1 (pre-flotetuzumab dose)
- Cycle 1 Day 7 (pre-week 2 infusion)
- Cycle 1 Day 14 (pre-week 3 infusion)
- Cycle 1 Day 21 (pre-week 4 infusion)
- Cycle 1 Day 28 (with C1D28 bone marrow biopsy)
- Cycle 2 Day 1 (pre-flotetuzumab)
- Cycle 2 Day 7 (pre-week 2 infusion)

- Cycle 2 Day 14 (pre-week 3 infusion)
- Cycle 2 Day 21 (pre-week 4 infusion)
- Cycle 2 Day 28 (with C2D28 bone marrow biopsy)
- At the time of disease relapse/progression.

These de-identified samples will be analyzed at a later time point at the discretion of the principal investigators and/or MacroGenics.

## 8.0 PHARMACEUTICAL INFORMATION

### 8.1 Flotetuzumab

#### 8.1.1 Flotetuzumab Description

Flotetuzumab is a CD123 x CD3 bi-specific antibody-based molecular construct referred to as a DART molecule. Its purpose is to bring into close proximity immune effector cells bearing the CD3 antigen, which is a component of the T cell antigen receptor complex, and target cells bearing the CD123 antigen, which is a component of the interleukin-3 receptor. As a result of opposing the two cells and activating the T cell, it is hypothesized that the neoplastic cells will be killed.

Flotetuzumab drug product (DP) is provided as a clear to slightly opalescent, colorless to pale yellow 5 mL sterile aqueous solution with a protein concentration of 0.1 mg/mL in a buffer composed of 10 mM sodium phosphate at pH 6.0, 150 mM sodium chloride, and 0.1 mg/mL polysorbate 80.

The concentration, function, and grade of each component in the DP are summarized below.

#### Flotetuzumab Drug Product Composition

Name of Ingredient	Concentration (mg/mL)	Nominal Amount per Vial (mg) a	Function
Flotetuzumab DS	0.10	0.50	Active ingredient
Sodium phosphate monobasic monohydrate	1.13	5.65	Buffer component
Sodium phosphate dibasic	0.26	1.3	Buffer component
Sodium chloride	8.78	43.9	Tonicifier
Polysorbate 80	0.10	0.50	Surfactant

Abbreviations: DS, drug substance

a. Amount based on 5.0 mL fill volume; vial contains approximately 0.30 mL overfill to deliver 5 mL.

### **8.1.2 Clinical Pharmacology**

The predicted mechanism of action of flotetuzumab is the creation of an immunological synapse between the leukemic blast target cell bearing CD123 and immune effector cells bearing the T cell-specific CD3 complex, leading to T cell activation and killing of the leukemic cell.

### **8.1.3 Pharmacokinetics and Drug Metabolism**

See Section 5.4 of the Investigator's Brochure for preliminary PK results from Study CP-MGD006-01. Overall, initial review of the data shows that there was high interpatient variability, but no obvious deviation of linearity across different doses. Preliminary analysis of flotetuzumab serum concentration indicates flotetuzumab PK is best fit by a two compartment PK model. In addition, flotetuzumab demonstrates a high clearance rate and a short half-life, as expected. Steady state volumes suggest there is high tissue distribution and/or binding. These data continue to be evaluated.

### **8.1.4 Supplier(s)**

Flotetuzumab will be provided by MacroGenics Inc.

#### Flotetuzumab Drug Product

Flotetuzumab Drug Product is supplied as 0.5 mg/5 mL (0.1 mg/mL) sterile aqueous solution packaged in a USP and Ph. Eur. conforming Type I borosilicate, 5 mL clear glass vial with a 20 mm FluroTec-coated 4432/50 gray butyl rubber serum stopper. The vial is sealed with a 20 mm TruEdge aluminum closure with a plastic overseal.

#### MGV004 Vehicle

The MGV004 IV Solution Stabilizer is supplied as a sterile solution of The MGV004 IV Solution Stabilizer is packaged in a USP and Ph. Eur. conforming Type I borosilicate, 50 mL clear glass vial with a 20 mm FluroTec and B2-40-coated 4023/50 gray butyl rubber serum stopper and sealed with a 20 mm TruEdge aluminum closure with a plastic overseal.

#### MGV002 Vehicle

MGV002 IV Solution Stabilizer is a sterile, clear-colorless solution presented in a single use glass vial. The MGV002 IV Solution Stabilizer is supplied as a sterile solution containing 0.9% sodium chloride solution with 0.1 mg/mL polysorbate 80. The MGV002 IV Solution Stabilizer is packaged in a USP and Ph. Eur. conforming Type I borosilicate, 50 cc clear glass vial with a 20 mm -4432/50 gray butyl rubber serum stopper and sealed with a 20 mm TruEdge aluminum closure with a plastic overseal.

### 8.1.5 Dosage Form and Preparation

Flotetuzumab DP is provided as a clear to slightly opalescent, colorless to pale yellow 5 mL sterile aqueous solution with a protein concentration of 0.1 mg/mL in a buffer composed of 10 mM sodium phosphate at pH 6.0, 150 mM sodium chloride and 0.1 mg/mL polysorbate 80.

The flotetuzumab dose solution can be prepared for administration from a syringe, an ambulatory cassette or a standard infusion bag. The administration options include the use of a syringe pump, dual ambulatory pumps, a single ambulatory pump, or standard IV infusion pump. Instructions for the preparation and administration of flotetuzumab are detailed in the Pharmacy Manual.

**Important:** Flotetuzumab MUST NOT BE ADMINISTERED AS AN IV PUSH OR BOLUS.

Flotetuzumab should not be mixed with other drugs or diluted with any solution other than MGV004 Vehicle or MGV002 Vehicle when administering the drug by 24-hour infusion.

Errors in dilution could result in fatal cytokine release syndrome; please refer to the Pharmacy Manual for further details on dosing schedule and dose preparation.

### 8.1.6 Storage and Stability

Vials containing flotetuzumab and MGV004 Vehicle or MGV002 Vehicle should be stored upright under refrigeration at 2°–8°C (36°–46°F) in an appropriate, locked room accessible only to pharmacy personnel, the Investigator, or a duly designated person. flotetuzumab and MGV004 Vehicle or MGV002 Vehicle must not be frozen. Monitor temperature and document and report any excursions as instructed in the Pharmacy Manual. Protect from light during storage as described in the Pharmacy Manual. DO NOT SHAKE. Use standard laboratory practices for avoidance of contact. Recommended safety measures for handling and preparation include masks, protective clothing, gloves, and vertical laminar airflow safety cabinet.

Follow standard hygiene practices, such as hand washing after handling. If material is released or spilled, soak up material with absorbent material and wash spill area thoroughly with soap and water. Dispose of collected material in accordance with applicable waste disposal regulations.

### 8.1.7 Administration

When administered by syringe pump or dual ambulatory pump configuration over 24 hours, flotetuzumab must be diluted prior to administration with appropriate custom vehicle, MGV004 Vehicle (2.2 mg/mL sodium phosphate monobasic

monohydrate, 0.52 mg/mL sodium phosphate dibasic anhydrous, 13.2 mg/mL benzyl alcohol, 4.25 mg/mL methyl 4-hydroxybenzoate sodium salt (methyl paraben), and 0.25 mg/mL polysorbate 80, pH 8.2 ) or MGV002 Vehicle (0.9% sodium chloride solution with 0.1 mg/mL polysorbate 80).

### 8.1.8 Special Handling Instructions

Precautions: Patients with known hypersensitivity to recombinant proteins, polysorbate 80, recombinant human serum albumin, benzyl alcohol, or any excipient contained in the flotetuzumab drug formulation should not receive flotetuzumab.

Infusion-related reactions including hypersensitivity/anaphylactic/anaphylactoid reactions or cytokine release syndrome may occur. Precautions for the management of these reactions should be observed during flotetuzumab administration.

## 9.0 DATA SUBMISSION SCHEDULE

Case report forms with appropriate source documentation will be completed according to the schedule listed in this section.

Case Report Form	Submission Schedule
On-Study Form Concomitant Meds Form Medical History Form Treatment History Form	Prior to starting treatment (meds given to treat CRS and ICANS collected throughout treatment)
Treatment Form	Every cycle
Acute GVHD form Chronic GVHD form	C1D1, C1D28, C2D7, C2D14, C2D21, C2D28, Follow-up
Toxicity Form Stopping Rules form	Continuous
Treatment Summary Form	Completion of treatment
Follow Up Form	Every 6 months for 2 years
Research Bone Marrow Collection Form	Baseline, C1D14, C1D28, C2D28, suspected disease relapse or progression.
Response Assessment Form	Baseline, C1D28, C2D28, end of treatment
Progression Form	Time of disease progression
Death Form	Time of death
MedWatch Form	See Section 13.0 for reporting requirements

## 10.0 MEASUREMENT OF EFFECT

Disease activity will be assessed using CBC and peripheral blood cell morphological examination, examination of bone marrow biopsy, and physical examination. For AML, modifications to the Revised Recommendations of the International Working Group for Diagnosis (IWG), Standardization of Response Criteria, Treatment Outcomes, and Reporting Standards for Therapeutic Trials in Acute Myeloid Leukemia will be used. See table below.

Complete remission (CR)	Bone marrow blasts <5%; absence of circulating blasts and blasts with Auer rods; absence of extramedullary disease; ANC $\geq 1.0 \times 10^9/L$ (1000/ $\mu$ L); platelet count $\geq 100 \times 10^9/L$ (100,000/ $\mu$ L), transfusion independence
CR with incomplete hematologic recovery (CRi)	All CR criteria except for residual neutropenia ( $< 1.0 \times 10^9/L$ [1000/ $\mu$ L]) or thrombocytopenia ( $< 100 \times 10^9/L$ [100,000/ $\mu$ L])
Morphologic leukemia-free state (MLFS)	Bone marrow blasts <5%; absence of blasts with Auer rods; absence of extramedullary disease; no hematologic recovery required
Partial remission (PR)	All hematologic criteria of CR; decrease of bone marrow blast percentage to 5 to 25%; and decrease of pretreatment bone marrow blast percentage by at least 50%
Stable disease (SD)	Absence of CR, CRi, PR, MLFS; and criteria for PD not met
Progressive disease (PD)	Evidence for an increase in bone marrow blast percentage (>50% over baseline), and/or increase of absolute blast counts in the blood (>50% to $> 25 \times 10^9/L$ ) without differentiation syndrome, or new extramedullary disease

Time to response (first or best response) will be calculated from the time of first dose of study drug to the time of initial response. Response duration and time to response will be calculated for patients who achieve an objective response. Progression free survival and overall survival will be calculated as the time from the start of the first dose of study drug until the occurrence of disease progression or death from any cause, respectively.

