### 3.0 STUDY POPULATION

#### 3.1 Inclusion Criteria

1. Histologically or cytologically confirmed relapsed acute myeloid leukemia (AML) or myelodysplastic syndrome (MDS), including any AML subtype, except acute promyelocytic leukemia (APL), and including AML that has evolved from a previous MDS or MPN.
2. Patients must have peripheral blast count  $\leq 20,000/\text{mm}^3$ . Use of hydroxyurea to control blast count is permitted.
3. Patients must be status post allo-HCT (including: matched related, matched unrelated, haploidentical, mismatched unrelated; and cord blood HCT).
4. Eastern Cooperative Oncology Group (ECOG) performance status (PS)  $\leq 2$  (see Appendix A).
5. Adequate organ function, defined as:
  - a. Hepatic transaminase (both alanine aminotransferase (ALT) and aspartate aminotransferase (AST) levels  $\leq 2.5$  times the institutional upper limit of normal (ULN),
  - b. Total bilirubin level  $\leq 1.5$  times the ULN (unless the patient has a history of Gilbert's Syndrome, in which case, total bilirubin must be  $\leq 2.5$  times the ULN),
  - c. Creatinine clearance of  $\geq 50$  ml/min.
  - d. Adequate organ reserve including cardiovascular (ejection fraction within institutional normal limits), pulmonary (baseline pulmonary function test [PFT]: carbon monoxide diffusion capacity in the lung [DLCO]  $> 50\%$ , forced expiratory volume in 1 second [FEV1]  $> 70\%$ ), renal, and hepatic functioning sufficient, in the judgment of the Investigator, to undergo therapy.
  - e. Normal thyroid function or stable thyroid tests on supplementation, except euthyroid sick syndrome.
6. Recovery from toxicities of clinical consequence attributed to previous chemotherapy to CTCAE v4.0 Grade  $\leq 1$  (i.e., certain toxicities such as alopecia will not be considered in this category).

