**Table 2: Response Criteria**

Complete remission (CR)	Bone marrow blasts <5%; absence of circulating blasts and blasts with Auer rods; absence of extramedullary disease; ANC $\geq 1.0 \times 10^9/L$ (1000/ $\mu$ L); platelet count $\geq 100 \times 10^9/L$ (100,000/ $\mu$ L), transfusion independence
CR with incomplete hematologic recovery (CRi)	All CR criteria except for residual neutropenia ( $<1.0 \times 10^9/L$ [1000/ $\mu$ L]) or thrombocytopenia ( $<100 \times 10^9/L$ [100,000/ $\mu$ L])
Morphologic leukemia-free state (MLFS)	Bone marrow blasts <5%; absence of blasts with Auer rods; absence of extramedullary disease; no hematologic recovery required
Partial remission (PR)	All hematologic criteria of CR; decrease of bone marrow blast percentage to 5 to 25%; and decrease of pretreatment bone marrow blast percentage by at least 50%
Stable disease (SD)	Absence of CR, CRi, PR, MLFS; and criteria for PD not met
Progressive disease (PD)	Evidence for an increase in bone marrow blast percentage (>50% over baseline), and/or increase of absolute blast counts in the blood (>50% to $>25 \times 10^9/L$ ) without differentiation syndrome, or new extramedullary disease

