### 5.3 Response Assessments

Bone Marrow Biopsy (BM Bx) will be performed at the following timepoints for disease assessments and correlative assessments:

- Screening/Baseline BM Bx: performed prior to starting on treatment.
- Cycle 1 D14 (+/- 3 days) BM Bx mid-Cycle 1 (correlative assessments only, no disease response assessment, collected at PI's discretion only).
- Cycle 1 D28 (+/- 3 days) BM Bx following completion of Cycle 1.
- Cycle 2 D28 (+/- 3 days) BM Bx following completion of Cycle 2.
- Final BM Bx performed at the time of suspected disease relapse or progression.

Responses will be assessed via IWG Criteria (Table 2).

See Section 7.0 for additional details regarding bone marrow biopsy schedule and correlative assessments.

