### 11.2 Primary Endpoint

The primary endpoint will be efficacy assessed via composite endpoint of CR and CRi (Cycle 1 Day 28 assessment).

Efficacy Endpoint will be defined as a combined endpoint of complete response (CR) and complete response with incomplete hematologic recovery (CRi), per International Working Group criteria (Table 2, and above.)

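### Table 2 sets CR/CRi by an absolute marrow threshold for every patient, so a narrow group of low-blast MDS entrants could already meet CRi at screening and count as responders if unchanged

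*Combined protocol and SAP*

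**What the plan says.** **Who enters.** Section 3.1, item 1, admits "Histologically or cytologically confirmed relapsed acute myeloid leukemia (AML) or myelodysplastic syndrome (MDS"). Its only blast criterion is a ceiling on peripheral blasts. Section 3.2, item 8, excludes relapse confined to extramedullary sites, so some marrow involvement is needed, but no percentage is given. Appendix B (IPSS-R) includes marrow blast bands of 2% or less and of more than 2% to under 5%, so the protocol itself recognises low-blast MDS.

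**How response is scored.** Section 10.0 presents its table as "For AML, modifications to the Revised Recommendations of the International Working Group" and gives no MDS criteria. Section 5.3 says, without restriction by disease, "Responses will be assessed via IWG Criteria (Table 2"). Section 11.2 states "The primary endpoint will be efficacy assessed via composite endpoint of CR and CRi", "per International Working Group criteria (Table 2, and above").

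**What the table asks for.** CR starts from "Bone marrow blasts <5%; absence of circulating blasts and blasts with Auer rods; absence of extramedullary disease", then adds neutrophil and platelet limits and transfusion independence. CRi is "All CR criteria except for residual neutropenia" or thrombocytopenia. Neither refers to the screening marrow. PR does: it needs a "decrease of pretreatment bone marrow blast percentage by at least 50" per cent.

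**What is absent.** Sections 5.5, 11.2, 11.7 and 11.8 do not say how to count a patient who already meets CR or CRi at screening.

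**The concern.** An absolute threshold measures response only if patients start on the wrong side of it. An AML relapse with a raised blast count does. An MDS relapse need not, because its diagnosis does not depend on 5% blasts. The same opening exists for an AML relapse enrolled below 5%, since Section 3.1 ties relapse to no blast figure.

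The decision thresholds are small numbers: 2 of 15 to continue and 6 of 25 to claim activity. A single response that reflects entry status rather than treatment effect therefore matters. There is no control arm in which the same artefact would appear and cancel. Such a patient would count both toward passing the futility look and toward the final claim.

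**Working it through.** **Inputs.** Section 11.3: 25 patients, null rate 10%, target 30%, 80% power, alpha 0.05, Simon minimax. Section 11.4: 15 patients in stage 1, continue with at least 2 responses. For the final threshold, Section 11.4 attaches 6 responses to the 15 patients, while Appendix I attaches them to the end of the study. I use 6 of 25, because 6 of 15 alone would give only about 28% power.

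**1. The plan's own figures.** With X the stage 1 responses,

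P(stop) = P(X ≤ 1), and P(success) = Σ over x = 2 to 15 of P(X = x) × P(Bin(10, p) ≥ 6 − x).

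- P(stop) at p = 0.10: 0.9^15 + 15 × 0.1 × 0.9^14 = 0.2059 + 0.3432 = 0.549 (plan: 55%).
- P(stop) at p = 0.30: 0.035 (plan: under 5%).
- P(success): 0.0328 at p = 0.10 and 0.8017 at p = 0.30.

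The design reproduces.

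**2. Automatic responders.** Let k of the 25 be counted as CRi whatever happens, a of them in stage 1, the others responding at 10%. Then

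P(success | a) = Σ over x with x + a ≥ 2 of P(Bin(15 − a, 0.10) = x) × P(Bin(10 − k + a, 0.10) ≥ 6 − k − x),

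averaged with weights C(15, a) × C(10, k − a) / C(25, k) for random position among the 25.

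- k = 1: 0.60 × 0.0847 + 0.40 × 0.0820 = 0.0836.
- k = 2: 0.35 × 0.1927 + 0.50 × 0.1908 + 0.15 × 0.1786 = 0.190.
- k = 3: 0.374 by the same sum.

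| Automatic responders | Chance of at least 6/25, random position | Same, all in stage 1 |
|---|---|---|
| 0 | 3.3% | 3.3% |
| 1 | 8.4% | 8.5% |
| 2 | 19.0% | 19.3% |
| 3 | 37.4% | 38.0% |

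**3. Futility stop.** With one such patient in stage 1, the trial stops only if none of the other 14 respond: 0.9^14 = 0.229. With two in stage 1 it cannot stop. Position matters: if there are two among the 25, the chance that both fall in the first 15 is C(15,2)/C(25,2) = 105/300 = 0.35.

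**4. Sensitivity.** Step 2 assumes full persistence of CRi to Day 28. If one such patient persists with probability 75% and otherwise counts as a non-responder, the result is 0.75 × 0.0836 + 0.25 × 0.0272 = 0.070, where 0.0272 is the success chance with that patient fixed as a non-responder.

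The model also matters. Instead of fixing k, one can fold these patients into a single response rate, p = k/25 + (1 − k/25) × 0.10. That gives 11.2%, 24.8% and 41.8% for k = 1, 2, 3 at full persistence, and 8.4%, 16.7% and 27.5% at 75%.

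**5. Power after the fix.** With k patients fixed as non-responders at random positions and the others at 30%, power is 76.6%, 72.6% and 68.1% for k = 1, 2, 3. For k = 1: 0.60 × 0.7648 + 0.40 × 0.7681 = 0.766.

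**The case against.** **The group is narrow and may be empty.** To meet CRi at entry a patient needs confirmed relapse after transplant and, at once, under 5% marrow blasts, no circulating blasts or Auer rods, no extramedullary disease and transfusion independence. The documents give no MDS share, low-blast share or transfusion status. This stands, and it is why the figures are conditional.

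**Persistence is not assured.** The patient must still be transfusion independent after a 28-day cycle, and Section 11.5.1 provides for prolonged Grade 4 cytopenia as a toxicity. A rise from, say, 2% to 4% blasts would also meet the progression criterion of more than 50% over baseline. This stands: full persistence is the worst case.

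**The benchmark may contain similar patients.** The titles of both sources cited for the 10% rate name AML and MDS. If those sources scored low-blast MDS the same way, part of the artefact is already in the null. The documents do not show this either way.

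**Section 10.0 limits the table to AML.** Read that way, the primary endpoint is undefined for enrolled MDS patients, which also needs repair. Sections 5.3 and 11.2 point to the table applying to everyone.

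**Investigators would recognise such a case.** Disease response is assessed at screening and a baseline Response Assessment Form is required (Section 9.0). Section 5.2 speaks of patients who have achieved CR/CRi. Cases are therefore identifiable, but no rule says how to count them.

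**Conclusion.** The gap in definition is established from the text: following the plan exactly, unchanged disease in a patient of the kind described scores as a primary-endpoint success. Its size is not established. The 8.4%, 19.0% and 37.4% rest on an assumed 1, 2 or 3 such patients, full persistence to Day 28, a 10% rate in everyone else, and a benchmark free of similar patients.

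A reader might infer that MDS patients in general are automatic responders, that the trial's type I error is in fact inflated, or that the futility rule is disabled. The documents support none of these. Transfusion dependence or circulating blasts at entry is enough to keep a patient out of CRi. The number affected may be zero, which leaves 3.3%. One such patient in stage 1 lowers the futility-stop chance from 55% to 23%; only two or more in the first 15 remove it.

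In the worst case a single patient is enough to pass the planned 5% level, so the rule should be written down. With an unknown and possibly empty group, the point ranks below must-fix.

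**What to change.** Add to Sections 5.5 and 11.2, with a cross-reference in Section 11.4 and Appendix I: a patient whose screening assessment, as recorded on the baseline Response Assessment Form, already meets Table 2 CR or CRi stays in the denominator, is not counted as a CR/CRi responder for the primary endpoint or the futility rule, and is described separately. Patients with under 5% screening blasts who do not meet CR or CRi at entry, for example because of circulating blasts or transfusion dependence, are scored as usual; they can genuinely achieve CRi. A blanket requirement of at least 5% screening blasts would wrongly deny them a response.

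Report the Cycle 1 Day 28 CR/CRi rate for AML and MDS separately beside the pooled rate.

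**Cost.** No new data are needed. Each affected patient lowers power: from 80.2% to 76.6%, 72.6% or 68.1% for 1, 2 or 3 patients when the others respond at 30%. A real benefit in such a patient does not count toward the primary endpoint. The change also alters the primary-endpoint numerator of an open-label trial already at Amendment 8, so it should be fixed in writing before the primary analysis, with the number of affected patients disclosed. With the rule in place, the chance of reaching 6 of 25 when the others respond at 10% does not exceed 3.3%.
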